| MedDRA | Medical Dictionary for Regulatory Activities |
| MCH | Mean corpuscular hemoglobin |
| MCHC | Mean corpuscular haemoglobin concentration |
| MCV | Mean corpuscular volume |
| NK | Natural Killer |
| PBMC | Peripheral blood mononuclear cells |
| PCR | Polymerase chain reaction |
| PEG | Polyethylene-glycol |
| PHA | Phytohemagglutinin |
| PK | Pharmacokinetic |
| PRBC | Packed red blood cells |
| PT | Preferred term |
| PT | Prothrombin time |
| PTT | Partial thromboplastin time |
| qPCR | Quantitative polymerase chain reaction |
| RBC | Red blood cell(s) |
| RCL | Replication competent lentivirus |
| SAE | Serious Adverse Event |

| | |
|------|--------------------------------------|
| SAS® | Statistical Analysis System® |
| SCID | Severe combined immunodeficiency |
| SOC | System Organ Class |
| TCR | T-cell receptor |
| TREC | T-cell receptor excision circle |
| UCLA | University of California Los Angeles |

1 Introduction

The primary objective of this clinical study is to further explore the safety and efficacy of OTL-101, an autologous, genetically modified CD34+ HSC based gene therapy for the treatment of ADA-SCID. The study will also be supportive of the analytical CMC comparability studies between the fresh and cryopreserved OTL-101 formulations. The following clinical outcomes, which are known to be good predictors of survival and event free survival: RBC ADA >0 Units, absolute CD3+ T-cell counts $\geq 200/\text{mm}^3$, and peripheral blood samples positive for vector sequences by qPCR ($>1/10,000$ cells), will be assessed as part of an interim analysis following completion of the 6 month follow-up visit.

2 Study Design

This is a prospective, non-randomized, single-cohort, longitudinal, single-center, clinical study designed to assess the efficacy and safety of OTL-101 cryopreserved formulation administered in ADA-SCID subjects aged between ≥ 30 days to < 18 years of age, who are not eligible for an HLA-matched sibling/family donor and meeting the inclusion/exclusion criteria. This study aims to recruit 10 evaluable subjects.

The aim of this clinical study is also to assess the success of treatment at the subject level (“responder analysis”) 6 months post GTMP administration, using predictive criteria for overall survival and event free survival and to compare data obtained from clinical studies using the fresh formulation of OTL-101.

Eligible subjects will be hospitalized to undergo the harvesting of autologous CD34+ cells. A backup harvest of non-transduced CD34+ cells will be obtained during the harvesting procedure to be used in the event of i) product damage during the thawing of the GTMP that would prevent infusion of the GTMP although the patient has already been conditioned or ii) lack of engraftment/hematopoietic reconstitution 42 days post infusion of the protocol treatment. A failure of hematologic reconstitution is defined as at least two of the following: absolute neutrophil count (ANC) $< 200/\text{mm}^3$, platelets $< 20,000/\text{mm}^3$ without transfusions, haemoglobin (Hb) $< 8.0 \text{ g/dl}$ without transfusions on three independent and consecutive determinations over at least 10 days beyond Day 42 from initial GTMP infusion.

The protocol treatment is a cryopreserved formulation of autologous CD34+ hematopoietic stem cells transduced ex vivo with EFS LV encoding for the human ADA gene (OTL-101). To enable the release of the GTMP for infusion, the cryopreserved OTL-101 product must meet various quality control criteria for safety, identity, viability, purity and potency. If OTL-101 meets the acceptance criteria and is released, the subjects will be readmitted for conditioning with busulfan. The OTL-101 product will be infused after a minimal interval of at least 24 hours following the completion of busulfan administration. Subjects may remain as an in-patient following autologous transplantation for approximately three to 35 days.

For subjects who have successfully received the OTL-101 product, PEG-ADA ERT will be discontinued at Day+30 (+/-3) after the transplant. After their discharge from hospital, the subjects will be seen at regular intervals to review their history, perform examinations and draw blood samples at Months 1, 3, 6, 9, 12, 18, and 24. Any medically-indicated interventions will be determined at these visits. Hematopoietic reconstitution will be assessed at Day 42, and in the event of no reconstitution the backup HSC sample will be administered. Hematopoietic reconstitution will be reassessed at the Month 6 visit and if there is still no evidence of cellular recovery, the subject will be given ERT and/or HSCT, if available, and deemed appropriate by

the Investigator. After Month 24 visit, the subjects will have completed the study and may enter a long-term follow-up study.

3 Study Schedule

Table 1: Schedule of Events – Screening to Day 24

| Study Period | Screening | Pre-harvest Assessment | Bone Marrow Harvest | Baseline | Conditioning | | OTL-101 Treatment | Short-term Follow-up | | | | | | | |
|-------------------------------------|----------------------------|--------------------------------|---------------------------------|----------------|----------------|--------------|-------------------|----------------------|-------|-------|--------|--------|--------|--------|---|
| | | | | | 3 ¹ | 3 | | 3 | 3 | 3 | 3 | 3 | 3 | 3 | 3 |
| Visit number | 1 | 2 ¹ | 2 | 3 ¹ | 3 | 3 | 3 | 3 | 3 | 3 | 3 | 3 | 3 | 3 | 3 |
| Assessment number | | A | B | C | D | E | F | G | H | I | J | K | L | M | |
| Visit window | | | | | | | | +/-2 days | | | | | | | |
| Day | Within 60 days of Visit 2B | Up to 5 days prior to Visit 2B | Approx 30 day prior to Visit 3F | Day-10 to -4 | Day -4 to -3 | Day -2 to -1 | Day 0 | Day 1 | Day 4 | Day 8 | Day 11 | Day 15 | Day 19 | Day 24 | |
| Informed Consent/Assent | X | | | | | | | | | | | | | | |
| Eligibility check | X | | | | | | | | | | | | | | |
| Demographic Data | X | | | | | | | | | | | | | | |
| Medical History | X | X | | | | | | | | | | | | | |
| Physical examination | X | X | | | X | | | | | | | | | | |
| Vital Signs | X | | | | X | | | X ² | | | | | | | |
| Weight (kg) | X | X | | | | X | | | | | | | | | |
| Height (cm) | X | | | | | | | | | | | | | | |
| Biochemistry sample ³ | X | X | | | X | | | X | X | X | X | X | X | X | |
| Hematology sample ⁴ | X | X | | | X | | | X | X | X | X | X | X | X | |
| PT or PTT/INR | X | X | | | X | | | | | | | | | | |
| PB or BM cytogenetics ⁵ | X | | | | | | | | | | | | | | |
| HIV-1/Hep B/Parvo B19 | X | | | | | | | | | | | | | | |
| Serum pregnancy test ⁶ | X | X | | | X | | | X | | | | | | | |
| Urinalysis ⁷ | X | X | | | X | | | | | | | | | | |
| ECG | X | | | | | | | | | | | | | | |
| Echocardiogram | X | | | | | | | | | | | | | | |
| Chest X-ray ⁸ | X | | | | | | | | | | | | | | |
| Pulse oxymetry | X | | | | X | | | | | | | | | | |
| Biopsy of skin lesions | X | | | | | | | | | | | | | | |
| ADA-SCID diagnosis confirmation | X | | | | | | | | | | | | | | |
| Questionnaire/QoL scale | X | | | | | | | | | | | | | | |
| Infectious episodes | X | | | | X | | | | | | | | | | |
| Adverse events | | X | X | X | X | X | X | X | X | X | X | X | X | X | |
| Concomitant Medication ⁹ | | X | X | X | X | X | X | X | X | X | X | X | X | X | |
| Type and cross PRBC | | X | | | | | | | | | | | | | |
| Bone marrow harvest | | | X | | | | | | | | | | | | |

| Study Period | Screening | Pre-harvest Assessment | Bone Marrow Harvest | Baseline | Conditioning | | OTL-101 Treatment | Short-term Follow-up | | | | | | |
|--|----------------------------|--------------------------------|---------------------------------|-----------------|-----------------|-----------------|-------------------|----------------------|-------|-------|--------|--------|--------|--------|
| | | | | | 3 ¹ | 3 | | 3 | 3 | 3 | 3 | 3 | 3 | 3 |
| Visit number | 1 | 2 ¹ | 2 | 3 ¹ | 3 | 3 | 3 | 3 | 3 | 3 | 3 | 3 | 3 | 3 |
| Assessment number | | A | B | C | D | E | F | G | H | I | J | K | L | M |
| Visit window | | | | | | | | +/-2 days | | | | | | |
| Day | Within 60 days of Visit 2B | Up to 5 days prior to Visit 2B | Approx 30 day prior to Visit 3F | Day-10 to -4 | Day -4 to -3 | Day -2 to -1 | Day 0 | Day 1 | Day 4 | Day 8 | Day 11 | Day 15 | Day 19 | Day 24 |
| PRBC transfusion | | | X | | | | | | | | | | | |
| Immune function ¹⁰ | | | | X ¹¹ | | | | | | | | | | |
| PBMC banking for RCL | | | | X ¹² | | | | | | | | | | |
| Serum banking for RCL | | | | X ¹² | | | | | | | | | | |
| Erythrocyte ADA enzymatic activity | | | | X ¹² | | | | | | | | | | |
| Erythrocyte deoxyadenine nucleotide levels | | | | X ¹² | | | | | | | | | | |
| Busulfan administration | | | | | X | X | | | | | | | | |
| PK samples | | | | | X ¹³ | X ¹⁴ | | | | | | | | |
| OTL-101 administration | | | | | | | X | | | | | | | |
| 1. Subjects will be admitted to the hospital for Visits 2 and 3. 2. During the infusion of OTL-101 vital signs will be monitored according to standard institute protocols. 3. Biochemistry samples will include the assessment of parameters listed in Table 3. Albumin ALT, AST, ALP will be measured at all time points indicated in this table. Total bilirubin, total protein, creatinine, blood urea, sodium, potassium, chloride, and calcium will be measured at screening, baseline, Day 1 and all follow-up visits (Month 1 to Month 24). Magnesium and phosphate will be measured only at pre-harvest and baseline time points. 4. Hematology samples will include the assessment of parameters listed in Table 3 and will be measured at all time points indicated in this table. 5. If cytogenetic testing was not performed on cells from amniocentesis, assessment should be by karyotype, CGH, and WES 6. Serum pregnancy tests are required in females of child-bearing potential at screening, prior to bone marrow harvest, prior to conditioning (Busulfan) treatment, and before the infusion of OTL-101. Any positive test will immediately result in the withdrawal of the subject from the study and should be reported as per guidance in Section Error! Reference source not found. 7. Urinalysis will include the assessment of parameters listed in Table 3 and will be measured at all time points indicated in this table. Any abnormalities detected on dipstick at Screening, Pre-harvest and Baseline will require repeat dipstick and microscopic examinations. 8. If there is any evidence of severe lung disease on the screening chest X-ray, a CT scan is required in order to establish if the subject meets any of the specified pulmonary exclusion criteria defined in Section Error! Reference source not found. 9. Standard post-transplant medication will be administered from Day 0 and recorded in the eCRF. 10. Immune function will be assessed absolute numbers of CD3+, CD4+ and CD8+ T-lymphocytes, CD19+ B-lymphocytes and CD56+/CD16+ (or CD56+/CD3-) NK cells, CD4+/CD45RA+ (naïve) and CD4+/CD45RO+ (memory) T cells, TREC levels, TCR Vβ usage, lymphocyte response to PHA (if sufficient cells), and serum immunoglobulin (IgG, IgA, IgM). 11. The immune function tests required for Visit 3, Assessment C can be performed at any point after provision of consent/assent and prior to Busulfan administration in younger subjects if deemed appropriate by the Investigator. 12. These test can be performed at anytime following BM harvest (Visit 2: Assessment B) and prior to OTL-101 administration (Visit 3: Assessment F) in younger subjects if deemed appropriate by the Investigator. | | | | | | | | | | | | | | |

| Study Period | Screening | Pre-harvest Assessment | Bone Marrow Harvest | Baseline | Conditioning | OTL-101 Treatment | Short-term Follow-up | | | | | | | |
|---|----------------------------|--------------------------------|---------------------------------|----------------|--------------|-------------------|----------------------|-------|-------|-------|--------|--------|--------|--------|
| | | | | | | | 3 ¹ | 3 | 3 | 3 | 3 | 3 | 3 | |
| Visit number | 1 | 2 ¹ | 2 | 3 ¹ | 3 | 3 | | | | | | | | |
| Assessment number | | A | B | C | D | E | F | G | H | I | J | K | L | |
| Visit window | | | | | | | | | | | | | | |
| Day | Within 60 days of Visit 2B | Up to 5 days prior to Visit 2B | Approx 30 day prior to Visit 3F | Day-10 to -4 | Day -4 to -3 | Day -2 to -1 | Day 0 | Day 1 | Day 4 | Day 8 | Day 11 | Day 15 | Day 19 | Day 24 |
| 13. PK blood samples are required at the end of Busulfan infusion, +1, 2, 4, 8, and 13 hours post-infusion (+/- 15 minutes). These values will be used to determine the second dose of Busulfan. | | | | | | | | | | | | | | |
| 14. One PK blood sample is required immediately before the second dose of Busulfan is administered, and then at the end of Busulfan infusion, +1, 2, 4, 8, and 13 hours post-infusion (+/- 15 minutes). | | | | | | | | | | | | | | |
| Abbreviations: ADA=adenosine deaminase, ALP=alkaline phosphatase, ALT=alanine aminotransferase, AST=aspartate aminotransferase, BM=bone marrow, CGH= Comparative Genome Hybridization, CT=computer tomography, ECG=electrocardiogram, eCRF=electronic case report form, HIV=human immunodeficiency virus, IgA=immunoglobulin A, IgG=immunoglobulin G, IgM=immunoglobulin M, INR=international normalized ratio, NK=natural killer, PB=peripheral blood, PBMC=peripheral blood mononuclear cells, PHA= Phytohemagglutinin, PK=pharmacokinetic, PRBC=packed red blood cells, PT=prothrombin, PTT=prothrombin time, QoL=quality of life, RCL= Replication Competent Lentivirus, SCID=severe combined immunodeficiency, TCR= T-cell receptor, TREC= T-cell receptor excision circle, WES= whole exome sequencing. | | | | | | | | | | | | | | |

Table 2: Schedule of Events – Month 1 to Month 24

| Follow-up Period | Month 1 (Day 30) | Day 42 ¹ | Month 3 | Month 6 | Month 9 | Month 12 | Month 18 | Month 24 | ET |
|---|---------------------|---------------------|-------------|-------------|-------------|-------------|-------------|-------------|-----|
| Visit number | 4 | 5 | 6 | 7 | 8 | 9 | 10 | 11 | N/A |
| Visit window | +/- 1 week | +/- 1 week | +/- 2 weeks | +/- 2 weeks | +/- 2 weeks | +/- 4 weeks | +/- 4 weeks | +/- 4 weeks | |
| Physical examination | X | | X | X | X | X | X | X | X |
| Vital Signs | X | | X | X | X | X | X | X | X |
| Weight (kg) | X | | X | X | X | X | X | X | X |
| Height (cm) | X | | X | X | X | X | X | X | X |
| Biochemistry sample ² | X | X | X | X | X | X | X | X | X |
| Hematology sample ³ | X | X | X | X | X | X | X | X | X |
| Questionnaire/QoL scale | | | | X | | X | X | X | X |
| Infectious episodes | X | | X | X | X | X | X | X | X |
| Adverse events | X | X | X | X | X | X | X | X | X |
| Concomitant Medication ⁴ | X | X | X | X | X | X | X | X | X |
| Record IgG and PEG-ADA therapy received | X | X | X | X | X | X | X | X | X |
| Immune function ^{5,6} | X | | X | X | X | X | X | X | X |
| Serum banking for RCL | | | X | X | | X | | X | X |
| Vector integration analysis | | | X | X | | X | X | | |
| Leukaemia assessment ⁷ | | | | X | | X | X | X | X |
| T-cell proliferation to PHA | | | | X | X | X | X | X | X |
| Antibodies to tetanus toxoid | | | | | | X | X | X | X |
| Presence of ADA gene in PBMC/granulocytes and/or lineage-sorted cells | | | X | X | | X | | X | X |
| RCL assay in PBMC | | | X | X | | X | | X | X |
| ADA enzymatic assay | X | | X | X | X | X | X | X | X |
| Deoxyadenine nucleotides in RBC | X | | X | X | X | X | X | X | X |
| Responder assessment ⁸ | | | | X | | | | | |

1. Day 42 assessment will use laboratory parameters to confirm if hematologic reconstitution has occurred. If this has not happened by Day 42 rescue medication, as per standard institute procedure, will be implemented. Any treatment administered to the subject will be recorded in the eCRF.
 2. Biochemistry samples will include the assessment of parameters listed in Table 3. Albumin ALT, AST, ALP will be measured at all time points indicated in this table. Total bilirubin, total protein, total protein, creatinine, blood urea, sodium, potassium, chloride, and calcium will be measured at screening, baseline, Day 1 and all follow-up visits (Month 1 to Month 24). Magnesium and phosphate will be measured only at baseline and the conditioning time points.
 3. Hematology samples will include the assessment of parameters listed in Table 3 and will be measured at all time points indicated in this table.
 4. Standard post-transplant medication will be administered from Day 0 and recorded in the eCRF.

5. Immune function will be assessed by absolute numbers of CD3+, CD4+ and CD8+ T-lymphocytes, CD19+ B-lymphocytes and CD56+/CD16+ (or CD56+/CD3-) NK cells, CD4+/CD45RA+ (naïve) and CD4+/CD45RO+ (memory) T cells, TREC levels, TCR V β usage, lymphocyte response to PHA (if sufficient cells), and serum immunoglobulin (IgG, IgA, IgM).
6. If IgG treatment is stopped, immunoglobulin levels will be required every month for the first 3 month after discontinuation. This is to ensure IgG levels hold before commencing vaccinations as per standard institute protocols.
7. A blood sample will be taken unless clinical/hematologic findings indicate potential leukoproliferation, whereby a bone marrow sample will be required. In addition to the time points specified in this table, this assessment should be performed if the nrLAM-PCR criteria is fulfilled (see Section **Error! Reference source not found.**).
8. Responder assessment includes: erythrocyte ADA enzyme activity, immune reconstitution, and gene-marked granulocytes as described in Section **Error! Reference source not found.**

Abbreviations: ADA=adenosine deaminase, ALP=alkaline phosphatase, ALT=alanine aminotransferase, AST=aspartate aminotransferase, eCRF=electronic case report form, ET=early termination, IgA=immunoglobulin A, IgG=immunoglobulin G, IgM=immunoglobulin M, N/A=not applicable, NK=natural killer, PBMC=peripheral blood mononuclear cells, PCR=polymerase chain reaction, PEG= polyethylene-glycol, PHA= Phytohemagglutinin, QoL=quality of life, RBC=red blood cell, RCL= Replication Competent Lentivirus, TCR= T-cell receptor, TREC= T-cell receptor excision circle.

4 Study Objectives

4.1 Primary Objectives

There are two primary objectives for this study:

- The success of treatment at the subject level (“responder analysis”) 6 months post OTL-101 infusion, defined as:
 - Evidence of erythrocyte ADA enzyme activity above baseline/pre-treatment level (>0 Units),
 - Evidence of immune reconstitution (absolute number of CD3 cells $\geq 200/\text{mm}^3$),
 - Detectable gene-marked granulocytes by differential polymerase chain reaction (dPCR)/qPCR ($\geq 1/10,000$ cells).
- Overall survival and event free survival at 12 months among ADA-SCID subjects treated with a cryopreserved formulation of OTL-101.
 - Overall survival is defined as the proportion of subjects alive.
 - Event-free survival is defined as the proportion of subjects with no “event”, an “event” being:
 - the resumption of PEG-ADA ERT
 - the need for a rescue allogenic HSCT, or
 - death.

4.2 Secondary Objectives

The secondary objectives to be evaluated among ADA-SCID subjects treated with a cryopreserved formulation of OTL-101 include:

- confirmation of the overall survival and event free survival at 24 months,
- safety evaluation including infection rates,
- quality of life, and
- immune response.

4.3 Exploratory Objectives

Exploratory objectives include the measurement of biological correlates of efficacy including:

- percentage of gene marking in peripheral blood granulocytes,
- vector integration analysis,
- quantification of clonal diversity of vector integrants,
- T-cell receptor excision circle (TREC) and fluorescence-activated cell sorting (FACS) for T-cell receptor (TCR) V- β family use,
- ADA enzyme activity in erythrocytes, total adenine nucleotides in erythrocytes, and
- immune reconstitution.

5 Endpoints

5.1 Primary Endpoints

Primary endpoints for this study are:

- Response to OTL-101 treatment at 6 months post infusion based on the following parameters and their thresholds:
 - Erythrocyte ADA enzyme activity above baseline/pre-treatment level (>0 Units),
 - Absolute CD3+ T-cell counts $\geq 200/\text{mm}^3$, and
 - Peripheral blood samples positive for vector sequences by qPCR ($\geq 1/10,000$ cells).
- Subjects must meet all three criteria. Subjects not meeting one or more of these criteria will be designated a failure (non-responder) and will be withdrawn from the study. This data will be used for comparison with subject data from the ongoing Phase I/II study using the fresh formulation.
- Overall survival and event free survival at 12 months post GTMP administration.
 - Overall survival is defined as the proportion of subjects alive.
 - Event-free survival is defined as the proportion of subjects with no “event”, an “event” being:
 - resumption of PEG-ADA ERT, or
 - the need for a rescue allogenic HSCT, or
 - death.

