Study Evaluations:	
Primary endpoints for this study include:
 
 Evaluation of OTL-101 at 6 months post infusion, in support of CMC assessing comparability of cryopreserved and fresh formulations, evaluation of therapy success for each subject based on the following parameters and their thresholds: 
 Erythrocyte ADA enzyme activity above baseline/pre-treatment level (>0 Units), Absolute CD3+ T-cell counts \geq200/mm³, and Peripheral blood samples positive for vector sequences by qPCR(\geq1/10,000 cells). Subjects must meet all three criteria. Subjects not meeting these criteria will be designated a failure (non-responder) and will be withdrawn from the study. This data will be used to compare subject data from one of the ongoing Phase I/II studies using the fresh formulation. Evaluate the overall survival and event free survival 12 months post OTL-101 infusion. Overall survival is defined as the proportion of subjects alive. Event-free survival is defined as the proportion of subjects alive with no “event”, an “event” being the resumption of PEG-ADA ERT or the need for a rescue allogenic HSCT, or death. 
Secondary endpoints include:
 
 Evaluate the overall survival and event free survival 24 months post OTL-101 infusion. Immunoglobulin Replacement therapies prior to and after gene therapy.

	
• Performance outcomes and quality of life will be measured by the Karnofsky/Lansky scale and questions relevant to general well-being, school attendance and ability to practice sports, respectively.• Rates of severe infections/ opportunistic infectious episodes, defined as infections requiring hospitalization or prolonging hospitalization and/or documented infections by opportunistic pathogens (i.e. interstitial pneumonia, intractable diarrhoea).• Response to tetanus vaccination.• Immune reconstitution: T and B cell reconstitution. 
The exploratory endpoints will include laboratory correlates of efficacy that will be used to assess the level of gene correction, engraftment and immune reconstitution as exploratory endpoints..

Safety Evaluations:	The safety and tolerability of OTL-101 will be assessed throughout the study by evaluating AEs, clinical laboratory test results, vital signs measurements, electrocardiogram (ECG) and physical examination results, and concomitant medication usage.

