9.3.1 Primary Efficacy Endpoints

The primary efficacy endpoints for this study include treatment success at 6 months post OTL-101 infusion, and overall survival and event-free survival at 12 months post OTL-101 infusion.

Treatment success at 6 months post OTL-101 infusion, will be performed in support of CMC assessing comparability between cryopreserved and fresh formulations. Evaluation of the success of therapy will be based on the following parameters and their thresholds:

- a) Erythrocyte ADA enzyme activity above baseline/pre-treatment level (>0 Units),
- b) Absolute CD3+ T-cell counts $\geq 200/\text{mm}^3$, and
- c) Peripheral blood samples positive for vector sequences by qPCR($\geq 1/10,000$ cells).

Treatment will be deemed successful in subjects meeting all three above thresholds. These subjects will be designated as “responders”. Those subjects failing to meet at least one of the above thresholds will be considered to be “non-responders.”

Overall Survival is defined as the time-to death from the OTL-101 infusion if death occurred, or to the date of the last evaluation if death did not occur. If no death occurred, the subject’s data will be considered censored at the last evaluation.

Event Free Survival is defined as the time-to event from the OTL-101 infusion if an event occurred, or to the date of the last evaluation without an event if no event occurred. If no event occurred, the subject’s data will be considered censored at the last evaluation. Event is defined as any of the following:

- Death
- Returning to PEG-ADA ERT
- Need of rescue HSCT

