8.3.1.2 Overall Survival at 12 Months

Overall survival will be evaluated using the time in months from transplant to either the subject’s death or their last evaluation calculated as:

$$12 * (\text{date of death/last evaluation} - \text{date of transplant}) / 365.25.$$

The number (%) of subjects who were still alive at 12 months post-transplant will be summarized. For the purpose of this analysis, any subject who withdrew from the study prior to 12 months, who was known to be alive at the last evaluation, will have a status of “unknown”. The proportion and exact 95% confidence interval (CI) for survivors at 12 months post-transplant will be calculated.

Overall survival will also be represented using a Kaplan-Meier curve for time to death. For the purpose of this analysis, any subject who withdrew from the study prior to 12 months and was known to be alive at the last evaluation will be censored at the date of their last evaluation. If appropriate, the proportion alive at 12 months and the associated 95% CI will be estimated from the Kaplan-Meier curve along with the median survival time (and interquartile range), if they can be estimated from the data.

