8.3.1.3 Event Free Survival at 12 Months

Event-free survival will be evaluated using the time in months from transplant to either the first event or their last evaluation calculated as:

$$12 * (\text{date of event/last evaluation} - \text{date of transplant}) / 365.25.$$

For the purpose of this analysis, the events of interest are:

- death;
- reinstitution of PEG-ADA ERT;
- requirement for a second transplant.

Event-free survival will be summarized in the same way as overall survival described in Section 8.3.1.2.

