8.3.2 Secondary Efficacy Endpoints

8.3.2.1 Overall and Event Free Survival at 24 Months

Overall and event-free survival at 24 months will be summarized in the same way as for the analyses at 12 months described in Sections 8.3.1.2 and 8.3.1.3.

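### Month-6 non-responders are withdrawn so that they can receive PEG-ADA or HSCT and are then censored, so Kaplan-Meier EFS misses rescue that first arises after withdrawal; Protocol 6.2.1.1 conflicts by keeping ERT restarters in follow-up

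*SAP*

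**What the plan says.** **Withdrawal.** SAP 5.1 applies to a subject who fails any of the three Month-6 criteria: "Subjects not meeting one or more of these criteria will be designated a failure (non-responder) and will be withdrawn from the study". The protocol synopsis (Study Evaluations) agrees: "Subjects not meeting these criteria will be designated a failure (non-responder) and will be withdrawn from the study". Protocol 5.1.7 (Month 6) and 7.1.1 repeat the withdrawal. Item 5 of Protocol 3.6.1 gives its purpose, which is to allow PEG-ADA or, where available, HSCT.

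**EFS.** EFS is a primary endpoint at 12 months and a secondary one at 24. Its events are death, return to PEG-ADA and the need for a rescue transplant, which SAP 8.3.1.3 words as "requirement for a second transplant". For handling, SAP 8.3.1.3 refers back to overall survival: "Event-free survival will be summarized in the same way as overall survival described in Section 8.3.1.2". SAP 8.3.1.2 then sets two rules:
- The proportion labels such a subject unknown, in the sentence that begins: "any subject who withdrew from the study prior to 12 months, who was known to be alive at the last evaluation, will have a status".
- For the Kaplan-Meier curve, a subject who withdrew before 12 months "and was known to be alive at the last evaluation will be censored at the date of their last evaluation".

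SAP 8.3.2.1 carries both forward: "Overall and event-free survival at 24 months will be summarized in the same way as for the analyses at 12 months". Protocol 9.3.1 is consistent. It measures EFS to the first event, "or to the date of the last evaluation without an event if no event occurred", and treats the latter subjects as censored.

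**Text pointing the other way.** The synopsis, Protocol 3.1 and SAP 2 describe ERT and/or HSCT at Month 6 as management within the study. Protocol 6.2.1.1 keeps a subject who restarts ERT in follow-up, but withdraws one who lacks reconstitution and could receive an allogeneic transplant. Protocol 3.6.1 ends by saying that endpoint evaluations go on for subjects already treated. SAP 8.1.2 tabulates rescue HSCT and other therapy among treatment failures.

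**The concern.** Kaplan-Meier estimation assumes that a censored subject has the same later risk as those still under observation. Here a subject is censored because he or she failed the markers that Protocol 2.1 and SAP 1 treat as predictors of EFS, and leaves for the stated purpose of receiving a treatment that defines the event. That is informative censoring built into a primary endpoint.

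The unobserved period after a Month-6 withdrawal is 6 months at the 12-month analysis and 18 months at the 24-month analysis. Because the texts conflict, the same clinical course can be an event or a censored observation depending on which paragraph the site follows. The analyses are descriptive, so what is at stake is the reported estimate and its interval, not a test.

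**Working it through.** **Inputs.** N = 10 treated, two-sided exact 95% intervals and a stated precision of 15% at 100% success (Protocol 9.4). Withdrawal, censoring and event rules as above. The documents give no expected Month-6 non-response rate.

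**1. The plan's own figure.** For 10/10 the exact lower limit is 0.025^(1/10) = 69.15%. The half-width is (100 − 69.15)/2 = 15.4%, which matches the stated 15%.

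**2. A non-responder traced through the text.**

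| Course | Text followed | EFS result |
|---|---|---|
| PEG-ADA restarted, or HSCT need recorded, by the withdrawal visit | Either | Event (no rule dates the HSCT need) |
| PEG-ADA restarted, subject kept in follow-up | Protocol 6.2.1.1 | Event |
| PEG-ADA restarted after withdrawal | SAP 5.1, Protocol 3.6.1 | Censored, not counted |
| HSCT need first recognised after withdrawal | SAP 5.1, Protocol 3.6.1 | Censored, not counted |

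Who is due rescue at Month 6 is also unclear. Protocol 5.1.7 can be read as requiring rescue only when all three criteria fail, while withdrawal follows from failing one. On that reading a partial non-responder leaves with no rescue due, and any later rescue falls in the last two rows. On the wording of 6.2.1.1, where reconstitution needs all three criteria, the two groups coincide.

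**3. Size in Kaplan-Meier EFS.** Let r be the number of rescues that occur after a Month-6 withdrawal but before the analysis time point, with no other events. The curve never drops, so it reads 100%. The true value is (10 − r)/10.

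| r | Kaplan-Meier as planned | All events counted (exact 95% CI) |
|---|---|---|
| 1 | 100% | 9/10 = 90% (55.5–99.7) |
| 2 | 100% | 8/10 = 80% (44.4–97.5) |
| 3 | 100% | 7/10 = 70% (34.8–93.3) |

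Three non-responders is also the number that halts enrolment under Protocol 3.6.1. If r = 1 and one of the other nine subjects has a recorded later event, Kaplan-Meier reads 8/9 = 88.9% against 8/10 = 80%.

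**4. The proportion.** With one subject of unknown status and no other events, all treated subjects in the denominator give 9/10 = 90%, which is not inflated. Only if unknowns were dropped would it read 9/9 = 100% (66.4–100).

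**5. How likely.** Let p be the non-response rate and m the share of non-responders whose first rescue event comes only after withdrawal, within the analysis period and with the site following the withdrawal text. Both are assumptions. The chance of at least one non-responder in ten is 1 − (1 − p)^10; the chance of at least one missed event is 1 − (1 − pm)^10.

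| p | At least one non-responder | Missed event, m = 0.25 | Missed event, m = 0.5 |
|---|---|---|---|
| 3% | 26% | 7% | 14% |
| 5% | 40% | 12% | 22% |
| 10% | 65% | 22% | 40% |

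For example, 1 − (1 − 0.05 × 0.5)^10 = 1 − 0.975^10 = 22.4%. The 3% row is close to an imperfect proxy in Protocol 1.3.3: one ERT restart in the UK study (93.3% EFS, so about 15 subjects by inference) and none of 18 at UCLA, or 1/33 = 3.0%. That is a restart rate with the fresh product, not Month-6 non-response.

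**The case against.** The strongest reply is that a miss needs several things to go wrong together.
- The HSCT event is the need, not the transplant, so it would normally be on record when the subject leaves.
- Protocol 6.2.1.1 keeps ERT restarters in the study, and the early termination visit (Protocol 5.1.8) documents PEG-ADA use.
- The SAP 8.1.2 table cannot be filled without collecting therapy given after failure.
- Protocol 3.6.1 says endpoint evaluations of treated subjects continue.
- The planned comparator study had no ERT restart among 18 subjects.

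Much of this stands, and it rules out some stronger readings. A reader might infer that therapy after withdrawal is never collected; SAP 8.1.2 implies that at least some is. A reader might infer that every non-responder drops out of EFS; an event recorded by the withdrawal visit counts. A reader might also infer that the EFS proportion is inflated. SAP 7.1 defines the efficacy population as all treated subjects, and with that denominator it is not. The SAP leaves out a clarifying sentence there, but does not adopt a wrong rule.

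The reply does not remove the core. SAP 8.1.2 is a disposition table, and nothing feeds it into EFS. The sentence in Protocol 3.6.1 concerns a halt to enrolment and sits below the item that withdraws non-responders, so it leaves the conflict unresolved. Attendance at the early termination visit is only encouraged, later follow-up is arranged if required (Protocol 4.4), and the registry needs separate consent under another protocol (5.1.9). Protocol 6.2.1.1 contradicts the withdrawal text and itself withdraws HSCT candidates.

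**Conclusion.** The concern holds. The withdrawal and censoring rules, applied as written, omit from Kaplan-Meier EFS any PEG-ADA restart after withdrawal and any HSCT need first recognised after withdrawal, at both 12 and 24 months. Protocol 6.2.1.1 would produce a different result for ERT restarters.

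Each missed event overstates Kaplan-Meier EFS by 10 points when ten subjects are treated and there are no other events. Across the assumed rates and shares, the chance of at least one such miss runs from 7% to 40%. There is no effect without non-responders, or when the event is recorded by the withdrawal visit. Confidence is high in the conflict and the missing link to EFS. It is moderate in the size of the bias, because neither the non-response rate nor the share of late rescues can be taken from the documents.

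**What to change.** 1. In SAP 5.1, the protocol synopsis and Protocol 3.6.1, 5.1.7 and 7.1.1, replace withdrawal of non-responders with wording to this effect: designated a treatment failure; remains in follow-up for survival, PEG-ADA and HSCT status to Month 24. Align Protocol 6.2.1.1, including its withdrawal of HSCT candidates.
2. In SAP 8.3.1.3 and 8.3.2.1, count a PEG-ADA restart at its start date and an HSCT need at the decision date as EFS events whenever they occur, including rescue recorded for the SAP 8.1.2 table.

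As a minor clarification, state that the survival and EFS proportions use all treated subjects (SAP 7.1), with unknown status shown as its own row.

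The cost is wording in both documents, one eCRF date for the HSCT decision, and status contacts for at most a few subjects, some of whom may be under transplant protocols. EFS may look less favourable.
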